10.2. Statistical Methodology

Analysis will be done on the per protocol population. For monocular outcomes, analysis will be performed on the study eye that was determined by randomization.

Superiority of Systane COMPLETE relative to Walgreens will be established if the mean SANDE score is significantly lower in the Systane COMPLETE group vs. Walgreens group.

Demographics, baseline characteristics, efficacy endpoints, and adverse events will be summarized descriptively. Summaries of these variables will include sample size, as well as the mean, median, standard deviation, minimum and maximum.

Primary Endpoint: Dry eye symptom frequency and severity as measured by the SANDE questionnaire change after 2 weeks of QID use (subject level). Total scores will be compared using a two-sample t-test.

The step-down methodology will be used on the other endpoints in the following order:

- Comparing corneal and conjunctival staining in the study eye before and after 2 weeks of QID use of their assigned drop (eye level). The corneal and conjunctival staining scores will be totaled from the 5 evaluation zones for analysis. Total scores will be compared using a two-sample ttest.
- Comparing Non-invasive TBUT times of the study eye in the two arms of the study, before and after 2 weeks of QID use of their assigned drop (eye level). Time will be compared using a two-sample t-test.
- Dry eye symptom frequency and severity as measured by the SANDE questionnaire after 1 week of QID use (subject level). Total scores will be compared using a two-sample t-test.

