3. GENERAL INFORMATION

Objective	To compare dry eye symptoms as well as corneal and conjunctival staining of Systane Complete Multi-Dose PF, versus the Walgreen's Lubricant Balance eye drop.		
	The hypothesis is that mild to moderate dry eye subjects will exhibit less frequent and severe dry eye symptoms after using Systane Complete Multi-Dose PF versus those who use Walgreen's Lubricant Balance.		
Test Article(s)	Systane Complete Multi-Dose PF Walgreen's Lubricant Balance		
Sample size	70 subjects		
Study Population	Subjects who currently have mild to moderate symptoms of dry eye.		
Number of sites	One		
Study Design	Single site, prospective, double-masked, randomized-controlled study with two arms		
Masking	Double-masked		
Variables	Primary: Dry eye symptom frequency and severity as measured by the SANDE questionnaire change after 2 weeks of QID use.		
	Exploratory:		
	 Comparing corneal and conjunctival staining before and after 2 weeks of QID use of their assigned drop. Comparing Non-invasive TBUT times of the subjects in the two arms of the study, before and after 2 weeks of QID use of their assigned drop. Dry eye symptom frequency and severity as measured by the SANDE questionnaire after 1 week of QID use. 		
Duration / Follow-up	Screening Visit to 2 weeks follow-up		

The study will be registered with clinicaltrials.gov.

The study will be conducted in compliance with the protocol, GCP and applicable regulatory requirements

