7.2. Inclusion Criteria

Subjects are eligible for the study if they meet the following criteria:

Note: Ocular criteria must be met in both eyes.

- Subjects who currently have mild to moderate symptoms of dry eye as defined by a screening SANDE score of 20-55 inclusive (equivalent to OSDI score of 12 32).²
- Subjects between the ages of 18-65.

- Subjects willing to comply with the prescribed regimen and schedule of eye drops.
- Subjects willing to attend all study visits.
- Subjects willing to discontinue any current artificial tear use 24 hours prior to the baseline study visit.

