8. STUDY DESIGN

8.1. Study Design

Single site, prospective, double-masked, randomized-controlled, two-arm study of the dry eye symptoms as well as corneal and conjunctival staining in subjects using 2 different eyedrops. Subjects will be assessed at a screening visit, and 2 follow-up visits. Clinical evaluations will include patient questionnaire, tear-breakup time, and slit lamp exam.

The primary outcome measure is Dry eye symptom frequency and severity as measured by the SANDE questionnaire change after 2 weeks of QID use.

Exploratory outcome measures are as follows:

- Comparing corneal and conjunctival staining before and after 2 weeks of QID use of their assigned drop.
- Comparing Non-invasive TBUT times of the subjects in the two arms of the study, before and after 2 weeks of QID use of their assigned drop.
- Dry eye symptom frequency and severity as measured by the SANDE questionnaire after 1 week of QID use.

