11. SAMPLE SIZE JUSTIFICATION

Assuming a difference in means between groups of 7 (SANDE) and a pooled standard deviation of 6, the study would require a sample size of 16 subjects for each group (total sample size of 32 subjects) to achieve a power of 90% and a level significance of 5%. To increase the study power and account for dropout, the sample size is being increased to 70 subjects (35 in each arm) to thoroughly characterize the performance of the drops.

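### Primary endpoint is the SANDE change, but the superiority rule is on the mean SANDE score: two primary t-tests fit the plan, and neither adjusts for baseline

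*Combined protocol and SAP*

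**What the plan says.** The summary in section 3 gives the endpoint as "Primary: Dry eye symptom frequency and severity as measured by the SANDE questionnaire change after 2 weeks of QID use", and section 8.1 repeats it: "as measured by the SANDE questionnaire change after 2 weeks of QID use". Section 10.2 pairs that endpoint with its test: "SANDE questionnaire change after 2 weeks of QID use (subject level). Total scores will be compared using a two-sample t-test".

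The sentence in section 10.2 that decides the trial is worded differently. Superiority "will be established if the mean SANDE score is significantly lower in the Systane COMPLETE group vs. Walgreens group". It mentions no visit and no change.

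Two other places bear on the reading:

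- The last step-down endpoint in section 10.2 carries the same test sentence, but its definition contains no change: "SANDE questionnaire after 1 week of QID use (subject level). Total scores will be compared using a two-sample t-test".
- The hypothesis in section 3 is about symptoms after treatment: subjects "will exhibit less frequent and severe dry eye symptoms after using Systane Complete Multi-Dose PF".

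Section 11 labels its inputs only as SANDE: "Assuming a difference in means between groups of 7 (SANDE) and a pooled standard deviation of 6". Table 15.1 schedules SANDE at all three visits, so a baseline value exists for every subject. No covariate appears anywhere in section 10.

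**The concern.** The endpoint definition points to a t-test on change from baseline. The superiority rule points to a t-test on the score, presumably at week 2. These are different tests with different variances, and they can give different answers on the same data. The phrase about total scores does not choose between them.

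This is the only test on which the superiority claim rests, and section 10.2 places the other endpoints behind it in a step-down order, so the ambiguity carries into everything tested afterwards. If the choice is open when the data are seen, the 5% error rate is not protected. A later reader could not tell from the plan which analysis was primary.

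Separately, both readings leave the baseline SANDE out of the model. That costs precision; it does not cause bias.

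**Working it through.** **Inputs from the plan.** Difference 7, SD 6, 90% power, 5% level, 35 per arm (section 11); alpha 0.05, sidedness not stated (section 10.3); entry SANDE 20 to 55 (section 7.2). **Assumed, because the plan does not give it:** correlation r between baseline and week-2 SANDE of 0.3, 0.5 or 0.7; equal SD at both visits; normal data unless stated.

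**1. The plan's own figure.** n per arm = 2 × [6 × (1.960 + 1.282) / 7]² = 15.4, rounded up to 16. This matches section 11 with a two-sided 5% level (a one-sided level gives 13). The result is 16 whichever quantity the SD of 6 describes, so the sample size does not reveal which test was intended.

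**2. The SDs of the three analyses.**
- Week-2 score: SD
- Change: SD × √(2(1 − r))
- ANCOVA residual: SD × √(1 − r²)

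The two t-tests have equal variance only at r = 0.5. The ANCOVA variance divided by the change variance is (1 − r²)/(2(1 − r)) = (1 + r)/2, and divided by the score variance it is 1 − r². Neither ratio exceeds 1.

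**3. Type I error if either test may be called primary.** With no true effect, the two test statistics have correlation √((1 − r)/2), that is 0.59, 0.50 and 0.39. The probability that at least one exceeds 1.96 in absolute value, from the bivariate normal distribution, is 8.8%, 9.1% and 9.4%. Simulation at 35 per arm (40,000 trials per setting) gave 8.7%, 9.3% and 9.6%; each test alone rejected in 4.8% to 5.2%. Rejection in favour of Systane was 4.3%, 4.6% and 4.8%, against a nominal 2.5%.

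**4. Power and disagreement at 35 per arm.** Disagreement means that one t-test has p < 0.05 and the other does not. Three values in a cell are for r = 0.3 / 0.5 / 0.7.

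| Setting | Score | Change | ANCOVA | Tests disagree |
|---|---|---|---|---|
| Difference 7, SD 6 at both visits | 99.8% | 98.2 / 99.8 / >99.9% | at least 99.8% | 1.8 / 0.5 / 0.3% |
| Difference 7, SD 10 (assumed) | 82% | 68 / 82 / 96% | 85 / 91 / 98% | 26 / 21 / 18% |
| Difference 4 (assumed), SD 6 | 78–79% | 64 / 79 / 94% | 82 / 88 / 97% | 28 / 24 / 22% |
| Difference 7, SD of change 6, baseline uniform on 20–55 (assumed) | 81.5% | 99.8% | 99.9% | 18.5% |

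With an assumed 30 completers per arm, the first row's disagreement becomes 3.6 / 1.2 / 0.6%.

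The last row tests the reading that the SD of 6 belongs to the change. The entry criterion is a SANDE score "as defined by a screening SANDE score of 20-55 inclusive". A uniform spread over that window has SD 35/√12 = 10.1. With the same SD at week 2, a change SD of 6 implies r = 1 − 36/(2 × 10.1²) = 0.82. The score test then has SD 10.1, and its power falls from 99.8% to 81.5%.

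**5. Why ANCOVA removes the conflict.** Write week-2 = a + τ × arm + β × baseline + error. Subtracting baseline from both sides gives change = a + τ × arm + (β − 1) × baseline + error. The treatment effect τ, its standard error and its p-value are unchanged; only the baseline coefficient moves. Score and change therefore give one and the same test.

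**The case against.** The best defence is that the plan calls the endpoint a change in all three places that define it, and that in section 10.2 the test sentence follows the definition directly. On this view *total scores* names the scale and not the contrast. The staining bullet supports this: its endpoint is worded as before and after two weeks, yet its test sentence also speaks of total scores. A *lower* mean could also loosely mean a more negative change.

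Part of this stands. Change is the more natural reading, and *total scores* is silent on the matter, so it is not positive evidence for a week-2 test. But the same sentence follows the week-1 endpoint, where no change is defined, and the superiority rule still refers to a mean score. Nothing else in the document overrides that rule.

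Three further points are fair, and they limit the finding:

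- The inflation arises only if the test is chosen after the data are seen.
- Under the protocol's own difference and SD, with the SD belonging to the score, the practical effect is small and power is not the issue. The larger disagreement rates need inputs that the plan does not give.
- An unadjusted t-test is valid under randomization, so the missing covariate is a loss of precision and not an error.

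**Conclusion.** The concern holds. The endpoint and the superiority rule name different quantities, no passage says which prevails, and the sample size calculation is compatible with both.

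The exposure is a two-sided type I error of about 9% instead of 5%, conditional on a choice made after seeing the data; this varies little over the assumed correlations. The effect on the trial's conclusion depends on what the SD of 6 describes. Disagreement between the tests is under 2% if it is the SD of the score at both visits, and about 18.5% if it is the SD of the change and baseline fills the entry window evenly. ANCOVA had power at least equal to the better t-test in every setting examined. This should be fixed before the data are unmasked, but it does not invalidate the design.

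**What to change.** In section 10.2, name one primary analysis: ANCOVA of the Visit 3 SANDE score on treatment arm, with Visit 1 SANDE as covariate. Declare superiority if the adjusted difference (Systane minus Walgreens) is below 0 with two-sided p < 0.05. Replace the references to the mean score and to total scores with this wording, and align sections 3, 8.1 and 10.2. In section 11, state whether the SD of 6 is for the week-2 score, the change or the ANCOVA residual.

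If a t-test is preferred, name the single quantity and visit it compares; that alone removes the type I error problem. Baseline adjustment of the exploratory staining, TBUT and week-1 SANDE comparisons is advisable but not essential.

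The cost is a change of wording. No new data are needed, the result is reported as an adjusted mean difference, and the model uses one more degree of freedom (67 instead of 68 with 35 per arm). The size of the precision gain depends on a correlation that the plan does not give.

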6. OBJECTIVE(S)

To compare dry eye symptoms as well as corneal and conjunctival staining of Systane Complete Multi-Dose PF, versus the Walgreen's Lubricant Balance eye drop.

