7.3. Exclusion Criteria

v 1.0

If any of the following exclusion criteria are applicable to the subject or either eye, the subject should not be enrolled in the study.

- Ocular anterior segment infection, inflammation, abnormality, or active disease.
- History of herpetic keratitis or ocular surgery.
- Recent (within 1 year) thermal meibomian gland expression procedure including Lipiflow, iLux, or TearCare.
- Recent (within 1 year) blepharitis debridement procedure including BlephEx.
- Screening SANDE score > 55 (equivalent to OSDI score of >32).² This is indicative of a severe dry eye.
- Screening SANDE score < 20 (equivalent to OSDI score of <12).² This is indicative of a clinically normal eye.
- Screening non-invasive TBUT < 2 seconds, or > 10 seconds.³
- Screening NaFl score < 3 (clinically normal eye) or > 10 (severe dry eye).⁴
- Pregnant or lactating.
- Current use of contact lenses.
- Any change in eye drop regimen, whether OTC or RX in the last 90 days.

The principal investigator reserves the right to declare a patient ineligible or nonevaluable based on medical evidence that indicates they are unsuitable for the trial.

Pregnancy has a known effect on the stability of refractions and visual acuity. As such, subjects who become pregnant during the study will not be discontinued but their data may be excluded from analyses of effectiveness.

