9.3.2. Staining

Baseline corneal and conjunctival staining with sodium fluorescein and Wratten filter assessed OU using the Academy of Ophthalmology 5 quadrant scheme. Each quadrant will be graded (0-3) giving a total score of 0-15 per eye. Again, both eyes will be evaluated, but only the total score of the single, previously selected eye in the TBUT measurement will be used for statistical analysis.

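### Free improvement (minor): the exploratory staining and tear breakup time comparisons use unadjusted t-tests although every eligible subject has a baseline value that could serve as a covariate

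*Combined protocol and SAP*

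**What the plan says.** Section 10.2 sets a step-down order after the primary SANDE test: staining, then TBUT, then 1-week SANDE. For staining, as for SANDE, "Total scores will be compared using a two-sample t-test". For TBUT, "Time will be compared using a two-sample t-test". No ANCOVA, regression model or covariate appears anywhere in the document.

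The analysed quantity is left open. The TBUT endpoint reads "Comparing Non-invasive TBUT times of the study eye in the two arms of the study, before and after 2 weeks of QID use", and the staining endpoint is worded similarly. Either could mean the Visit 3 value or the change from baseline.

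The baseline exists for both endpoints:
- Table 15.1 schedules both at Visit 1 and Visit 3, and section 9.3.2 states "Baseline corneal and conjunctival staining with sodium fluorescein and Wratten filter assessed OU".
- Both values decide eligibility under section 7.3. A subject is excluded for "Screening non-invasive TBUT < 2 seconds, or > 10 seconds", and likewise for a fluorescein score below 3 or above 10.

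Sections 3 and 8.1 label both endpoints exploratory. Staining is nevertheless part of the objective in section 6: "To compare dry eye symptoms as well as corneal and conjunctival staining of Systane Complete Multi-Dose PF, versus the Walgreen's Lubricant Balance eye drop".

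**The concern.** An unadjusted t-test fixes the weight given to baseline in advance: 0 if Visit 3 values are compared, 1 if changes are compared. ANCOVA estimates that weight from the data. When baseline predicts Visit 3 to some degree, a fixed weight usually leaves removable noise in the comparison.

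This matters a little more here than the exploratory label suggests. Staining is in the objective and comes first after the primary, so a real staining effect that is missed also stops formal testing of TBUT and 1-week SANDE. Section 11 sizes the trial on SANDE alone, so nothing shows that 70 subjects are enough for staining or TBUT.

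**Working it through.** **The plan's own figure.** Section 11 gives a SANDE difference of 7, SD 6, power 90% and significance level 5%. The normal approximation, two-sided, gives 2 × (1.960 + 1.282)² × 6² / 7² = 15.4, so 16 per arm and 32 in total, as stated. (An exact t calculation gives 89.1% power at 16 per arm and needs 17; a one-sided test would need 13.) The figure reproduces, which supports two-sided testing at 0.05, but it says nothing about staining or TBUT.

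**Inputs for staining and TBUT.**
- From the documents: 35 per arm (section 11), 1:1 allocation (8.3), alpha 0.05 (10.3).
- Assumed, because the documents give none: standardised effect 0.6 in Visit 3 SD units; correlation ρ between baseline and Visit 3; k = baseline SD / Visit 3 SD.

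**Variance of each analysis**, with Visit 3 variance set to 1:
- Visit 3 t-test: 1
- Change-score t-test: 1 + k² − 2kρ, which is 2(1 − ρ) when k = 1
- ANCOVA: 1 − ρ²

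The Visit 3 t-test exceeds ANCOVA by ρ². The change-score t-test exceeds it by (1 + k² − 2kρ) − (1 − ρ²) = (k − ρ)². Neither excess can be negative, so ANCOVA is at least as precise under both readings and for any k. Estimating the slope multiplies its variance by about 1 + 1/66 with 70 subjects. Against a Visit 3 t-test, break-even is therefore at ρ² = 1/67, or ρ about 0.12.

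ANCOVA also gives the same treatment estimate for the Visit 3 value and for the change: subtracting baseline from the outcome only shifts the fitted slope by 1.

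**Why k matters.** Entry limits baseline staining to 3–10 and baseline TBUT to 2–10 seconds. No such limit applies at Visit 3, where section 9.3.2 allows staining of 0–15. A baseline SD smaller than the Visit 3 SD is therefore plausible. k = 0.7 is an illustration, not a documented value.

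**Power** (noncentral t, two-sided 0.05, 35 per arm, effect 0.6):

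| ρ | Visit 3 t-test | Change, k = 1 | Change, k = 0.7 | ANCOVA | ANCOVA with slope cost |
|---|---|---|---|---|---|
| 0.2 | 69.7% | 49.9% | 61.4% | 71.4% | 70.7% |
| 0.3 | 69.7% | 55.2% | 66.7% | 73.7% | 73.0% |
| 0.5 | 69.7% | 69.7% | 79.5% | 81.5% | 80.9% |
| 0.7 | 69.7% | 89.1% | 93.4% | 93.4% | 93.0% |

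Example of the variances at ρ = 0.5: Visit 3 = 1; change = 1 + 1 − 1 = 1 for k = 1, and 1 + 0.49 − 0.70 = 0.79 for k = 0.7; ANCOVA = 1 − 0.25 = 0.75.

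**Gain of ANCOVA in power points**, before the slope cost, which takes off up to 0.7:
- over the Visit 3 t-test: 1.7, 4.0, 11.8 and 23.7 at ρ 0.2, 0.3, 0.5 and 0.7;
- over the change score at ρ 0.3, 0.5 and 0.7: 18.5, 11.8 and 4.3 with k = 1; 7.0, 2.0 and 0 with k = 0.7.

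**Sensitivity.** At ρ = 0.5 against the Visit 3 t-test, an effect of 0.3 gives 23.6% against 29.8%, and an effect of 1.0 gives 98.5% against 99.7%, so the gain shrinks at both ends. With an assumed 30 analysed per arm and effect 0.6, the figures are 62.8% and 75.1%: power falls under both methods, while the gain stays near 12 points.

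**The case against.** The strongest reply is that little depends on this. Both endpoints are exploratory, and the hypothesis, the superiority criterion and the sample size all rest on SANDE. Section 10.2 summarises every efficacy endpoint descriptively whatever the step-down does. All of that stands, and it is why the point is minor.

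The gain is also uncertain. Under equal SDs, ρ = 0.5 is where the two t-tests tie, so the 12-point gain over the better of them is a peak. Restricted entry ranges may lower ρ, which shrinks the gain over a Visit 3 test, and may lower k, which shrinks the gain over a change score. The 35 per arm includes a dropout allowance, and efficacy is analysed in per-protocol completers. These limits stand too.

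Three stronger readings are tempting and are not supported:
- A reader might infer that the t-tests are biased or inflate type I error. Allocation is randomised in permuted blocks, so they are valid; chance baseline imbalance adds noise, not bias.
- A reader might take losses of 12, or 18 to 24, points as what to expect. Those are favourable cases. For the change score they need equal SDs, which the one-sided effect of the entry limits makes doubtful.
- A reader might infer that baseline is ignored altogether. The before-and-after wording may mean a change score, which uses baseline by subtraction.

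What survives is that ANCOVA costs at most a fraction of a power point and can gain several.

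**Conclusion.** The point holds as a free improvement of minor severity. The plan leaves an available baseline out of two formally tested exploratory comparisons, one of which belongs to the stated objective. That ANCOVA is at least as precise does not depend on how the endpoint is read or on equal variances; its only cost is the slope estimate, visible when ρ is below about 0.12 or, for a change score, when ρ is close to k.

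The size cannot be fixed from the documents. At an assumed effect of 0.6 with 35 per arm it runs from nothing to about 24 power points, depending on ρ, k and the reading of the endpoint. The harm is lost efficiency on the step-down tests. It does not reach the primary SANDE conclusion, for which power at 35 per arm is about 99.8% under the plan's own inputs.

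**What to change.** In section 10.2, replace the t-test sentences for staining and TBUT with wording such as:

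> The study-eye total staining score at Visit 3 will be analysed by ANCOVA with treatment arm as a factor and the study-eye Visit 1 score as covariate. Study-eye non-invasive TBUT at Visit 3 will be analysed in the same way, with Visit 1 TBUT as covariate. Adjusted mean differences with 95% confidence intervals will be reported, and these tests will determine the step-down. Unadjusted t-tests will be supportive.

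State whether the supportive t-tests use the Visit 3 value or the change. Make the edit before unmasking, since a covariate chosen later is open to challenge.

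The cost is two sentences, one line of R per endpoint and one degree of freedom per model. It needs no new data, visits or subjects.
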